#### 9.5.9. Blinding

The appropriate SM, according to randomization, will be placed into bottles to be dispensed to the subject by an unblinded staff member (e.g., coordinator or pharmacist). Identity of treatment arm must not be disclosed to the site's blinded study staff or the Sponsor (or designee). An unblinded Clinical Research Associate (CRA) will monitor the SM records.

### 9.5.10. Concomitant Medications

For subjects who receive SM, concomitant medications and therapies that are ongoing as of the date of informed consent will be recorded on the Concomitant Medication CRF. The Investigator will record all concomitant medications, including over-the-counter medications, on the Concomitant Medication CRF. The Investigator will record the AE for which the concomitant medication was administered on the AE CRF.

## 9.5.11. Treatment Compliance

Records of SM and doses administered will be kept during the study by unblinded site staff. The unblinded CRA will review SM accountability during investigational site visits and at the completion of the study.

## 9.5.10. Change of Study Medication Dose

Subjects will be assigned to 1 of 2 treatment groups. All subjects will titrate to the maintenance dose of SM and will remain on SM for 6 weeks during the Maintenance Period. Down titration to the starting dose is allowed for subjects who cannot tolerate the maintenance dose, at the discretion of the Investigator in consultation with the Medical Monitor. Subjects who cannot tolerate study drug after dose-reduction should be removed from the study.

### 9.6. Data Quality Assurance

This study will be organized, performed, and reported in compliance with the protocol, Standard Operating Procedures (SOPs), working practice documents, and applicable regulations and guidelines. Site visit audits may be made periodically by the Sponsor or CRO's qualified compliance auditing team, which is an independent function from the study conduct team.

### 9.6.1. Data Collection

The Investigator (or designee) will enter the information required by the protocol into the CRF in accordance with the CRF Completion Instructions that are provided with the CRF. The CRA will visit each investigational site as frequently as documented in the monitoring plan to review the CRF for completeness and accuracy against the source documents. The CRA will highlight any discrepancies found in the documentation of study conduct and ensure that appropriate site personnel address the discrepancies. Procedures for data collection and correction will be discussed at the site initiation visit, routine monitoring visits, and will be included in the completion instructions.

### 9.6.2. Clinical Data Management

Data from the CRF and other external data (e.g., laboratory data) will be entered into or transferred to a clinical database as specified in the data management plan for this study. Quality control and data validation procedures will be applied to ensure the validity and accuracy of the clinical database.

### 9.6.3. Database Quality Assurance

The clinical database will be reviewed and checked for omissions, apparent errors, and values requiring further clarification using computerized and manual procedures. Data queries requiring clarification will be documented and returned to the investigational site for resolution. Only authorized personnel will make corrections to the clinical database, and all corrections will be documented in an audit trail. A quality assurance audit will be performed prior to database lock.

## 9.6.4. Bioanalytical Data Management and Quality Control

PK samples and requisition forms will be shipped by the Investigator to the central laboratory, and instructions will be detailed in the central laboratory manual. Analysis will be performed by means of a validated chromatographic method. Details on the analytical methodology, the method validation, and the analytical within-study quality control procedures will be included in the clinical study report for this protocol.

## 9.7. Statistical Methods

#### 9.7.1. Statistical and Analytical Plans

Tabular summaries of the data collected during the study will be presented to provide a general description of the subjects studied and an overview of the safety, efficacy, and PK results. Data from all investigational sites will be combined in the computation of these summaries, and summaries will be presented by treatment group.

As down titration from 300mg to 150mg is allowed for subjects who cannot tolerate the maintenance dose, those subjects will be treated as part of the 300mg arm while analyzing the data.

Continuous variables will be summarized using descriptive statistics (number of subjects, mean, standard deviation, median, and minimum and maximum values). Categorical (nominal) variables will be summarized using frequency tables (number and percentage of subjects in each category).

In addition to tabular summaries, subject data listings, as specified in Sections 16.2 and 16.4 of ICH E3, will be provided. Additional subject data listings to be provided for this study are listed under the relevant subsections below.

The full data analyses will be performed by the CRO after the study is completed and the database is locked. Statistical programming and analyses will be performed using SAS® and/or other validated statistical software as required.

The statistical analyses described in this section will be described in more detail in the Statistical Analysis Plan (SAP), which will be finalized prior to database lock and will be included in the clinical study report for this protocol. The final SAP will take into account any amendment to the protocol.

### 9.7.1.1. Analysis Populations

The safety population consists of all randomized subjects who take at least one dose of SM.

The intent-to-treat (ITT) population consists of all randomized subjects who took at least one dose of SM (i.e., the safety population), had baseline efficacy assessment, and had at least one post-baseline efficacy assessment.

The ITT population is the population for the efficacy analysis. Subjects will be analyzed according to treatment assigned.

The restricted ITT population consists of all ITT population subjects with at least 1 efficacy assessment after three weeks of treatment.

The PK population consists of all Safety population subjects with an evaluable PK profile.

#### 9.7.1.1.1. Demographic/Baseline Analyses

Demographic/baseline variables include age, sex, ethnicity, race, baseline height, baseline weight, and medical history. Tabular summaries of the demographic/baseline variables will be presented for the safety, ITT, and restricted ITT populations, except for medical history, which will be summarized for the safety population only.

#### 9.7.1.1.2. Study Medication

Tabular summaries of the treatment percent compliance rate and duration of treatment exposure to SM will be presented for the safety population. The number and percentage of subjects maintained on the target dose versus those reduced in dose during the Maintenance Period will be provided.

Analysis of treatment compliance and exposure will be performed separately for the Baseline and Randomization Period, Dose Treatment Period, and combined Baseline and Randomization and Dose Treatment Periods.

#### 9.7.1.1.3. Concomitant Medications

Concomitant medications will be assigned an 11-digit code using the WHO Drug Dictionary (WHO DD) drug codes. Concomitant medications will be further coded to the appropriate Anatomical-Therapeutic-Chemical (ATC) code indicating therapeutic classification. A tabular summary of concomitant medications by drug class will be presented for the safety population.

### 9.7.1.2. Efficacy Analyses

Efficacy analyses will be conducted for the ITT population. Where appropriate, a restricted ITT population may also be used.

Descriptive statistics will be presented for all efficacy variables by visit and treatment group.

All significance tests will be performed at the 0.05 level.

#### 9.7.1.2.1. Primary Efficacy Analysis

The primary efficacy measure is the investigator-rated CAARS Total ADHD Symptom Score which is the sum of the Inattention and Hyperactivity/Impulsivity subscales (18 items measured on 4-point scale: 0, 1, 2, and 3).

The changes from baseline to the endpoint (visit 8) in the investigator-rated CAARS Total ADHD Symptom Scores will be compared between the two treatment groups using the Wilcoxon rank-sum test or the two-sample t-test.

To confirm the results (sensitivity analysis), a mixed model repeated measures (MMRM) analysis will be conducted. MMRM analysis will contain fixed effect terms for treatment,

investigative site, visit, and interaction between treatment and visit. The model will include post-baseline values of the investigator-rated CAARS Total ADHD Symptom Score as the dependent variable with a random patient effect and baseline investigator-rated CAARS Total ADHD Symptom Score as a covariate and will use an unstructured covariance.

## 9.7.1.2.2. Secondary Efficacy Analyses

The following secondary efficacy analyses will be performed:

- 1. Initial efficacy of SPN-812V starting dose (150 mg/day) when compared to placebo as measured by changes in the investigator-rated CAARS Total ADHD Symptom Score from baseline at week 1 of treatment with starting dose will be analyzed with Wilcoxon rank-sum test or two-sample t-test
- Effectiveness of any SPN-812V dose when compared to placebo as determined by the weekly changes in the Clinical Global Impression – Improvement (CGI-I) score from baseline severity for 6-week treatment will be plotted as mean CGI-I change versus visit and analyzed using Wilcoxon rank-sum test or two-sample ttest
- 3. Clinical utility of SPN-812V study dose (300 mg/day) when compared to placebo as determined by the investigator's assessment of the changes in the Conner's Adult ADHD Rating Scale (CAARS) score from baseline at week 2, 3, 4, 5, and 6 of treatment will be analyzed with Wilcoxon rank-sum test or two-sample t-test
- 4. Study subject's perception of clinical benefit of SPN-812V study dose (300 mg/day) when compared to placebo as determined by changes in the self-rated Conner's Adult ADHD Rating Scale (CAARS) score from baseline at endpoint after 5-week treatment will be analyzed with Wilcoxon rank-sum test or two-sample t-test

### 9.7.1.2.3. Subgroup Analyses for Efficacy

Subgroup analyses for efficacy will be performed on categories of the following measures:

- Sex
- Race

for the ITT population for the investigator-rated CAARS Total ADHD Symptom Score. Subgroup analyses will also be carried out for the following subscales

- investigator-rated CAARS inattention subscale score
- investigator-rated CAARS hyperactivity/impulsivity subscale score

that together make up the CAARS Total ADHD Symptom Score

#### 9.7.1.3. Pharmacokinetic Analyses

Population PK data will be pooled across all subjects and analyzed using nonlinear mixed-effects modeling methods. The objective of the population PK analyses is to derive individual-specific estimates of apparent oral clearance (CL/F) but not to fully characterize the PK of this formulation of viloxazine.

## 9.7.1.4. Safety Analyses

Evaluation of safety will be performed for the safety population. Safety data that will be evaluated include AEs, clinical laboratory results, vital signs, ECGs, and physical examination findings.

## 9.7.1.4.1. Adverse Events

AEs will be classified into standardized medical terminology from the verbatim description (Investigator term) using the Medical Dictionary for Regulatory Activities (MedDRA). AEs will be presented in the summary tables by preferred term nested within System Organ Class (SOC). Verbatim description and all MedDRA level terms, including the lower level terms, for all AEs will be contained in the subject data listings.

Data for AEs will be analyzed using the treatment-emergent signs and symptoms (TESS) philosophy. TESS are defined as AEs that:

- emerge during treatment, having been absent at pretreatment, or
- reemerge during treatment, having been present at pretreatment but stopped prior to treatment, or
- worsen in severity during treatment relative to the pretreatment state, when the AE is continuous.

Only treatment-emergent AEs (TEAEs) from the study will be summarized in tables. TEAEs will be summarized by presenting, for each treatment group, the incidence of AEs. The incidence of TEAEs will be based on the numbers and percentages of subjects with TEAEs. Although a MedDRA term may be reported more than once for a subject, that subject will be counted only once in the incidence count for that MedDRA term.

Separate TEAE incidence tables will be presented for the Baseline and Randomization Period, Dose Treatment Period, and combined Baseline and Randomization and Dose Treatment Periods. For the combined Baseline and Randomization and Dose Treatment Periods, the incidence of TEAEs will also be presented by highest severity reported, closest relationship to SM reported, and the dose of SM at first occurrence. For treatment-related TEAEs only, i.e., those TEAEs classified as possibly or definitely related to SM, the incidence rates will also be summarized as described previously for all TEAEs. Listings (and tabular summaries, if warranted) of deaths, other SAEs, and other significant AEs, including AEs resulting in treatment discontinuation, will be provided.

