### 9.4.4.1.2. Criteria for Assessing Severity

The Investigator will evaluate the comments of the subject and the response to treatment in order that he/she may judge the true nature and severity of the AE. Severity refers to the accumulated intensity of discomfort / impairment of health since the last recording of AEs and will be assessed according to the following criteria:

Mild: Awareness of sign, symptom, or event, but easily tolerated

**Moderate:** Discomfort enough to interfere with usual activity and may warrant intervention

**Severe:** Incapacitating with inability to do usual activities or significantly affects clinical status and warrants intervention

The criteria for assessing severity are different from those used for seriousness (see Section 9.4.4.2. for the definition of an SAE).

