### 3.1.2 Dosing Period

Subjects who meet the requirements for study participation will be randomized and proceed to the Dosing Period which will last 6 weeks. Approximately 50 subjects will be randomized at a 1:1 ratio, using a centralized randomization system, to either SPN-812V or placebo. The first dose of SM should be taken the morning after the randomization visit. Subjects who do not tolerate the starting dose will be discontinued from the study.

The first dose of SM should be taken the morning after the randomization visit. Subjects will receive treatment at the 150 mg/day starting dose for one week. Subjects who do not tolerate the starting dose will be discontinued from the study.

Subjects who tolerated the starting dose will then be titrated to receive a study dose of 2x50 mg TID (300mg/day) and continue this treatment regimen for five weeks. Subjects who, after titration to the study dose, do not tolerate treatment at 300 mg/day, will be allowed, at any time, to down-titrate the dose to the 150 mg/day starting dose and continue treatment at the same dose until completion of the study. Subjects will return to the investigational site once a week to undergo safety and efficacy evaluations and to have SM compliance checked.

Subjects who have consented to participate in the optional PK sub study will be given a diary at Visit 7 on which to record time of SM doses taken prior to Visit 8. Subjects who are participating in the optional PK sub study will be given all efficacy assessments prior to blood draws or dosing on the PK day. For subjects not participating in the optional PK sub study, their last dose will be taken the evening before the End of Study Visit (Visit 8).

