### 6.1.1 Overall Study

Adverse events that occur or worsen after the first administration of study medication are considered treatment-emergent and will be summarized in tables. For missing information, the most conservative interpretation will be assumed. For example, if AE onset time is not collected, the AE starts on the first study dose date.

AEs will be summarized for each treatment group by presenting the incidence of AEs based on the number and percentage of subjects with AEs.

Table 14.3.1.1.1 will provide overall incidence of AEs for the Safety population. Table 14.3.1.1.2 will provide an incidence summary of AEs by System Organ Class, and Preferred Term for the Safety population.

Table 14.3.1.1.3 will provide an incidence summary of AEs by System Organ Class, Preferred Term, and Relationship to Study Drug for the Safety population. If a subject had two or more adverse events in the same system organ class (or with the same preferred term) with different relationships to study drug, then the event with the closest relationship to study drug will be used for that subject.

Table 14.3.1.1.4 will provide an incidence summary of AEs by System Organ Class, Preferred Term, and Severity for the Safety population. If a subject had two or more adverse events in the same system organ class (or with the same preferred term) with different levels of severity, then the event with the worst severity will be used for that subject.

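### The protocol's by-dose TEAE display shows an event that starts at 150 mg/day and worsens at 300 mg/day under 150 mg/day only, and the SAP text has no by-dose AE table

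*Protocol*

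**What the plan says.** Every active subject passes through both doses. SAP 3.1.2 states: "Subjects will receive treatment at the 150 mg/day starting dose for one week". The step to 300 mg/day for five weeks follows, with a return to 150 mg/day allowed for intolerance.

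Protocol 9.7.1.4.1 sets these rules for adverse events:

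- Counting: a term may be reported repeatedly, but "that subject will be counted only once in the incidence count for that MedDRA term".
- Worsening: a continuing event qualifies as treatment-emergent if it should "worsen in severity during treatment relative to the pretreatment state, when the AE is continuous".
- By period: "Separate TEAE incidence tables will be presented for the Baseline and Randomization Period, Dose Treatment Period", and for the two combined.
- Extra displays for the combined periods: incidence is also to be "presented by highest severity reported, closest relationship to SM reported, and the dose of SM at first occurrence".

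SAP 6.1.1 lists AE tables by treatment group: overall, by SOC and preferred term, by relationship, and by severity. SAP 6.1.2 repeats them by sex, race and ethnicity. For a subject with several severities in a class or term, "then the event with the worst severity will be used for that subject". SAP section 4 places all subjects randomized to active drug under the 300 mg/day group, whether or not the dose was later reduced. The SAP text names no AE table by dose and none by period. SAP section 8, on changes from the protocol, records no such omission.

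**The concern.** Safety is the primary objective. The protocol's Introduction calls the design dose-ranging and sets out to evaluate safety and tolerability at 150 or 300 mg/day. A reader with that question will turn to the one display that is expressly by dose. That display is keyed to onset, so it cannot show that an event tolerable in week 1 became worse after the step-up. The severity display keeps the worst grade but attaches no dose to it. Under the SAP text the reader would find no by-dose table at all. The study could then be reported without a clear account of the dose at which the worst events occurred.

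**Working it through.** **1. Follow one event.** Suppose a term is mild in week 1 at 150 mg/day, continues, and becomes severe at 300 mg/day.

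| Planned output | Where the event appears |
|---|---|
| Protocol, dose at first occurrence | Once, under 150 mg/day |
| Protocol, highest severity | Severe, with no dose stated |
| Protocol, tables by period | Unclear (see below) |
| SAP Table 14.3.1.1.4 | Severe, active arm (300 mg/day group), no dose |
| SAP 6.1.3 | Listed if serious, otherwise significant, or a cause of discontinuation, dose reduction or interruption; tabulated only if warranted |

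The period tables do not clearly fill the gap. Protocol Table 1 puts Visit 2 and Visits 3–8 under the Dose Treatment Period, and 9.4.1.3.1 describes the starting-dose week within that period. On that reading, the second period mixes both doses. SAP 4.5 equates the first period with the starting-dose week, but only for compliance and exposure. On either reading, no rule says whether a continuing event that worsens after week 1 counts again. SAP 6.1.1 treats events that occur or worsen after the first dose of study medication as treatment-emergent, but it does not attach them to a dose level.

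**2. How many subjects could be affected.** The documents give no AE rates, so these are assumptions. Let n = 25 (approximate arm size, protocol 9.7.2), p = share of the active arm with first onset of a given term in week 1 (assumed 10–40%), and w = share of those who worsen at 300 mg/day (assumed 10–50%).

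Subjects whose worsening is not shown at 300 mg/day = n × p × w:

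- Low: 25 × 0.10 × 0.10 = 0.25 (1 percentage point)
- Middle: 25 × 0.20 × 0.30 = 1.5 (6 points)
- High: 25 × 0.40 × 0.50 = 5 (20 points)

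In the middle case, if 20% of the remaining subjects first have the term at 300 mg/day, the 300 mg/day row is 25 × 0.80 × 0.20 = 4.0 by onset, and 4.0 + 1.5 = 5.5 if worsening is also counted.

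**3. Time at risk pulls the other way.** Without down-titration, 1 of 6 weeks (17%) is at 150 mg/day and 5 of 6 (83%) at 300 mg/day. (Protocol 9.5.7 speaks of 6 weeks of maintenance; that must be reconciled with the five weeks stated elsewhere, but it does not alter the argument.) Assume a constant weekly hazard h and no dose effect. First onsets are then 25 × (1 − e^(−h)) at 150 mg/day and 25 × (e^(−h) − e^(−6h)) at 300 mg/day:

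| h (assumed) | 150 mg/day | 300 mg/day | Share in week 1 |
|---|---|---|---|
| 0.02 | 0.50 | 2.33 | 17.5% |
| 0.05 | 1.22 | 5.26 | 18.8% |
| 0.10 | 2.38 | 8.90 | 21.1% |
| 0.20 | 4.53 | 12.94 | 25.9% |

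With no dose effect at all, crude counts by onset dose would make 300 mg/day look worse. The onset rule moves some information the opposite way. The documents do not allow the two to be netted, and the protocol defines no denominator by dose for this display.

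**The case against.** The strongest defence is that the display does what its label says: it reports dose at onset. It is one of three extra displays. The main tables are by treatment group, and there the example event is reported at its worst severity in the active arm. The protocol's safety endpoint and AE comparison with placebo concern either or any dose, so they do not change. Dose follows time in every subject, so no table can isolate a dose effect. The table shells are separate documents (SAP section 10) and may contain more than the SAP text.

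Much of this stands. The onset display is not in error as a record of onset, and no main comparison is affected. It does not answer the narrower point: the dose at which the worst severity was reached is clearly shown nowhere in the planned tables, and the SAP drops the protocol's by-dose and by-period tables without comment.

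A reader might infer more: that 300 mg/day will look better tolerated than it is, or that the order of the doses reverses. Such a case can be built. Assume 25% onset in week 1, 5% new onset per week later, and moderate-or-worse severity in 20% of cases at 150 mg/day and, independently, 40% at 300 mg/day.

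- By onset dose: 0.25 × (1 − 0.8 × 0.6) = 13% at 150 mg/day against 0.75 × (1 − 0.95^5) × 0.4 = 7% at 300 mg/day.
- By the dose at which that severity was first reached: 0.25 × 0.2 = 5% against 0.25 × 0.8 × 0.4 + 0.07 = 15%.

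The documents do not support that as a finding. None of these rates comes from them. The example needs severity cross-tabulated by onset dose, which the protocol does not clearly plan. The longer exposure at 300 mg/day pushes crude counts the other way.

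**Conclusion.** The gap is real but limited. In the protocol's supplementary by-dose display, worsening after the step-up is invisible at 300 mg/day, and no other planned table clearly supplies the dose at worst severity. The SAP text has no by-dose or by-period AE table and does not say that the protocol's were dropped. On the assumed rates the effect is 0.25 to 5 of 25 subjects per term, with 1.5 in the middle case. Whether the higher dose would look better or worse than it should is not determined. The conclusion rests on the SAP text alone, since the shells were not available. This is an inexpensive improvement to a descriptive safety table, not a threat to the main comparison with placebo.

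**What to change.** Keep the onset-dose display in protocol 9.7.1.4.1 and add a by-dose TEAE table to SAP 6.1.1, for example:

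> *TEAEs will be tabulated by dose level: 150 mg/day start, 300 mg/day, and 150 mg/day after reduction, with placebo shown by the matching capsule level. A subject is counted for a term at each level at which the term first occurs or worsens from its last recorded on-treatment severity. Highest severity is shown by the level at which it was reached. The number of subjects and the person-time at each level are given as denominators.*

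In SAP section 8, state what becomes of the protocol's by-period tables. If they are kept, define the periods for AE purposes and say whether a continuing event that worsens counts again.

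The assessment needed already exists in the protocol: 9.4.4.1.2 says "Severity refers to the accumulated intensity of discomfort / impairment of health since the last recording of AEs". A CRF completion note should ensure that a change in severity is recorded with its date, for instance as a new AE line.

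The cost is SAP wording, one table and that note. A subject can appear in more than one column, so columns will not sum to the total. The table remains descriptive, because dose is confounded with time on treatment.
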